11.4.3 Skin Reactions

In order to reduce the likelihood or severity of skin reactions in subjects, protection from light should be taken from the start of study drug treatment until three to four weeks after the discontinuation of treatment.

In the event of a skin reaction in a subject, the following formulations may be used as assessed by the investigator: steroid cream, topical or systemic anti-inflammatory drugs, topical

antihistamines, or vitamin A cream. Symptomatic measures may be taken if necessary.

Skin reactions should be recorded in the AE section of the eCRF and should contain the following information:

- Altered characteristics of skin reactions.
- CTCAE grade of skin reactions.
- If necessary, images should be taken to document skin reactions and these images should be reviewed by external experts.
- A skin biopsy may be performed if necessary.

11.4.4 Gastrointestinal Toxicity

Nausea and/or vomiting may be controlled by antiemetic therapy. If diarrhea is CTCAE Grade 3 or higher, or clinically significant, or intolerable, and is related to study medication in the opinion of the investigator, necessary management or dose modification may be conducted. Relevant information should be recorded in the AE section of the eCRF.

11.4.5 QTc Interval Prolongation

When a subject experiences prolongation of the mean QTcF interval (absolute QTcF > 500 msec, or > 60 msec from baseline) from 3 ECGs at rest, the dose should be interrupted and ECGs should be monitored routinely until recovery to baseline. If the event recovers to \leq CTCAE Grade 1 or to baseline (whichever is met first) within 2 weeks, the normal dose or reduced dose of the investigational product as shown in Table 7 may be resumed. If the normal dose is resumed, the subject should be closely monitored for 3 days, and if the same toxic effect occurs within the 3 days, a dose reduction should be considered. The above decision requires agreement between the investigator and the Sponsor's physician. If the event does not recover to \leq CTCAE Grade 1 or to baseline within 2 weeks, the subject should permanently discontinue treatment and follow-up should be continued until recovery of the toxicity. When an adverse event of QTc prolongation is required to be reported, the QTc interval will only refer to the QT interval corrected using the Fridericia's formula (QTcF).

11.4.6 Interstitial Lung Disease

If new or worsening pulmonary symptoms (e.g., dyspnea) or imaging abnormalities observed suggesting interstitial lung disease, it is recommended to interrupt the study treatment and notify the Sponsor.

All diagnostic results (including HRCT, blood and sputum cultures, hematology parameters) will be investigated by questionnaire. The investigators are strongly recommended to perform a thorough diagnostic workup on the patient to exclude alternative causes such as lymphatic

metastasis, infection, allergy, cardiac edema or pulmonary hemorrhage.

The diagnosis of interstitial lung disease should be considered when it is confirmed by a HRCT scan and respiratory symptoms due to other causes are excluded, and study treatment should be permanently discontinued. If the diagnosis of interstitial lung disease is excluded, the treatment may be resumed after consultation with the Sponsor's physician.

Subjects with established interstitial lung disease will permanently discontinue the study treatment.

12.0 Endpoint Evaluation and Statistical Analysis

12.1 Evaluation of Anti-Tumor Activity

12.1.1 Investigator's Assessment per RECIST 1.1

At each visit, the investigator will assess the patient's tumor status as CR, PR, SD, or PD per RECIST 1.1 compared to baseline and previous assessments based on the patient's status. Progression of TPs will be calculated by comparing with the nadir of tumor burden (i.e., the smallest sum of diameters previously recorded). In the absence of progression, tumor response (CR and PR) and stable disease (SD) will be calculated by comparing to baseline tumor measurements obtained prior to the initiation of treatment. Patients who cannot be assessed for tumor status will have PD if there is evidence of progression; the tumor status will be not evaluable (NE) if there is no evidence of progression. The analysis of the endpoints in this study will be based on the Investigator's assessment of tumor response per RECIST 1.1, and the management of subjects by the investigator will only be performed based on the results of this assessment.

12.1.2 Central Review

All imaging data collected during the study, including tests performed during unscheduled visits, should be assessed with an independent central review.

12.1.3 Progression-free Survival (PFS)

According to RECIST 1.1 ([Appendix D](#)), PFS is defined as the time period from the randomization to the occurrence of objective tumor progression assessed by the Investigator or death. In the absence of disease progression, radiographic tumor assessments will need to be collected until RECIST-defined disease progression, even if the patient has discontinued the treatment with HS-10296 or has received another anti-tumor therapy prior to disease progression.

A subject who does not have disease progression or is dead at the time of analysis will be censored at the last date of his/her last assessment as per the RECIST criteria. If a subject

experiences disease progression or death after 2 or more missing visits, the subject will be censored at the last date of his/her last assessment as per the RECIST criteria. The data derived from the progression-free survival are based on assessment date rather than visit date.

If a patient discontinues study treatment prior to progression and/or receives other treatments prior to progression, the patient will be continued to be followed up until evidence of objective disease progression as per RECIST 1.1. Worsening of symptoms will not be considered as an event of progression.

12.1.4 Objective Response Rate (ORR)

According to RECIST 1.1, ORR is defined as the percentage of patients achieving at least 1 CR or PR prior to progression.

The last evaluable data until disease progression or in the absence of disease progression will be recorded in the ORR assessment. However, any CR or PR occurring after discontinuation of study treatment and receiving further anti-tumor therapy will not be included in the ORR calculation.

12.1.5 Duration of Response (DoR)

Duration of response is defined as the time period from the date of the first response to the date of disease progression or death due to any cause. The end date of response should be consistent with the date used for PFS endpoints. The onset of the time to response is defined as the latest date of the visit on which the criteria for PR or CR is met for the first time. If a patient has no progression after response, the PFS censoring time will be used for the duration of response.

12.1.6 Disease Control Rate (DCR)

Disease control rate is defined as the proportion of patients with a best overall response of CR, PR, or SD.

12.1.7 Depth of Response (DepOR)

According to RECIST 1.1, depth of response (change in tumor size) is defined as the change in the sum of the longest diameters of target lesions in the absence of new lesions or progression of non-target lesions from baseline. The percentage change in tumor size for patients with measurable disease at baseline will be calculated using the percentage change in the sum of target lesion diameters from baseline at each visit. The best depth of response will be generated from all response evaluations prior to progression or prior to initiation of subsequent anti-tumor therapy.

12.1.8 Overall Survival (OS)

Overall survival is defined as the time period from the date of first dose to the date of death due

to any cause. A patient who survives to the time of statistical analysis will be censored at the time point the patient is last known to be alive.

12.2 Safety Evaluation

At the end of the study, all safety data will be summarized. All data from the start of treatment until 28 days after the last treatment will be summarized in the safety assessment. Data obtained prior to the initiation of treatment will be summarized but not included in the summary table of AEs.

The number of subjects with each AE will be summarized by Medical Dictionary for Regulatory Activities (MedDRA) system organ class (SOC), MedDRA preferred term (PT) and CTCAE grade. The number and percentage of subjects with AEs of different categories (e.g., the relationship to the investigational product, or CTCAE Grade 3 or higher) will be summarized by group. In addition, adverse events of each category will also be further summarized by MedDRA system organ class and preferred term by group. Serious adverse events will be separately summarized. The events of death will be tabulated in detail by subject.

Any AE that occurs prior to the subject's first dose (i.e., prior to Study Day 1) will be tabulated but will not be included in the summary tables of AEs. Any AE occurring during the specified 28-day follow-up period after a subject discontinues the study treatment will be included in the AE summary report; any AE that occurs after the subject discontinues the treatment with the investigational product and has received other further anti-tumor therapy during that follow-up period will be flagged in the data tables. Adverse events that occur during the 28-day follow-up period after the discontinuation of the investigational product will be tabulated separately and will not be included in the AE summary report. For subjects that can continue to derive benefit in the opinion of the Investigator after disease progression and continue to receive study treatment, the AEs occurred in these subjects will be tabulated separately and will not be included in the summary tables of AEs.

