6.2 Double-blind Design

This study will be conducted based on a double-blind design, i.e., from the start of randomization until disease progression as assessed by the investigator per RECIST 1.1, the information of the actual treatments will remain blinded to the subjects, the investigator, data analysts, the Sponsor, and all medical personnel involved in the treatment or clinical assessments.

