12.3.3 Safety Analysis

12.3.3.1 Adverse Event

AEs occurring from treatment initiation until 28 days after the last dose will be summarized in the safety evaluation. AEs that occur prior to the initiation of study treatment and those occurring 28 days after the last dose will not be included in the summary table of AEs.

Adverse events occurring post-dose will be summarized by treatment group, mainly including:

- 1) The number and proportion of patients with at least one AE;
- 2) The number and proportion of patients with at least one study drug-related AE;
- 3) The number and proportion of patients with at least one AE of higher severity (CTCAE Grade ≥ 3);
- 4) The number and proportion of patients with at least one study drug-related AE of higher severity (CTCAE Grade ≥ 3);
- 5) The number and proportion of patients with at least one SAE;
- 6) The number and proportion of patients with dose modifications due to AEs;
- 7) The number and proportion of patients who have withdrawn from the study due to AEs;
- 8) The number and proportion of patients who died due to AEs.

Adverse events will be summarized by system organ classes and preferred terms. All adverse events will be tabulated.

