##### **Progression follow-up for subjects who terminate treatment for reasons other than disease progression:**

- Solid tumor efficacy evaluation is performed once every 6 weeks (C1-C21) or 12 weeks (C23 and after) until the investigator evaluates disease progression based on RECIST 1.1
- ECOG PS scoring is performed once every 6 weeks (C1-C21) or 12 weeks (C23 and after) until the investigator evaluates disease progression based on RECIST 1.1
- Recording of concomitant medications: Only the detailed information of subsequent anti-tumor treatment is recorded until disease progression
- Subjects with disease recurrence before the completion of the 28-day safety follow-up after discontinuation of treatment should continue the safety follow-up until 28 days after discontinuation of treatment.

**Progression follow-up of subjects who continue to receive the investigational treatment (compassionate treatment) after disease progression:**

- It is recommended to conduct tumor evaluation based on RECIST 1.1 once every 6 weeks (C1-C21) or 12 weeks (C23 and after) until the investigator judges progression after compassionate treatment or medication is terminated before progression (for safety reasons or based on the investigator's judgment or the subject's decision)
- ECOG PS scoring is performed once every 6 weeks (C1-C21) or 12 weeks (C23 and after) until the investigator judges further progression or medication is terminated before progression (for safety reasons or based on the investigator's judgment or the subject's decision)
- Recording of concomitant medications: All concomitant medications, including anti-tumor therapy, until 28 days after the drug is terminated, after which only anti-tumor therapy is collected
- Recording of adverse events: For subjects who continue to receive the investigational treatment after progression, continue to collect their AEs and SAEs until 28 days after the drug is terminated, after which only AEs with no outcome and SAEs related to the investigational drug are collected.

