### **1.2.6. Blinding**

This trial adopts a double-blind design. From the start of randomization until the investigator evaluates disease progression based on the RECIST 1.1 criteria, the true status of treatment will be kept blinded from the subjects, the investigator, the data analysts, the sponsor, and all medical personnel involved in treatment or clinical evaluation.

In this study, randomization numbers and drug numbers will be obtained through the IWRS. The double-dummy technique is adopted to control the blinding of the drug. HS-10296 tablets and HS-10296 dummy tablets (as well as gefitinib tablets and gefitinib dummy tablets) will use completely identical packaging, administration methods, labeling, appearances, flavors, and odors to conceal the truth about the investigational drug. HS-10296 tablets and gefitinib dummy tablets are packaged together and gefitinib tablets and HS-10296 dummy tablets are packaged together. After uniform packaging, they are given drug numbers uniformly. The blind codes are stored in the IWRS and with the randomization specialist.

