### 5.1. Adverse events

Adverse events will be coded with MedDRA 23.0 or a higher version.

CTCAE (4.03) will be obtained for the rating of the seriousness of adverse events. AEs that occur from the start of treatment to within 28 days after the last treatment will be summarized in the safety evaluation. AEs occurring prior to treatment initiation and AEs occurring within 28 days after the last treatment are tabulated separately and will not be included in summary tables for AEs.

General principles to follow when summarizing adverse events:

- 1) Adverse events are summarized by treatment group and system organ class/preferred time (SOC/PT).
- 2) If the same subject has the same adverse event multiple times, the one with the highest correlation with the investigational drug will be used to summarize the investigational drug-related AE and the one with the highest severity will be used for the summary of adverse event seriousness.
- 3) Only adverse events during the randomized, double-blind treatment stage and not during the cross-treatment stage are included.

All of the AEs of each subject will be presented in a list.

Related to the investigational drug refers to “definitely related,” “possibly related,” and “unable to be determined.”

Serious adverse events will be summarized and tabulated individually.

The following summary results will be given:

- 1) Summary of all adverse events
- 2) All adverse events summarized by system organ class and preferred term
- 3) Investigational drug-related adverse events summarized by system organ class and preferred term
- 4) All common adverse events summarized by system organ class and preferred term
- 5) All common investigational drug-related adverse events summarized by system organ class and preferred term
- 6) Adverse events of CTCAE grade  $\geq 3$  summarized by system organ class and preferred term
- 7) Investigational drug-related adverse events of CTCAE grade  $\geq 3$  summarized by system organ class and preferred term
- 8) Serious adverse events (SAEs) summarized by system organ class and preferred term
- 9) Investigational drug-related serious adverse events (SAEs) summarized by system organ class and preferred term
- 10) Adverse events leading to permanent discontinuation summarized by system organ class and preferred term
- 11) Investigational drug-related adverse events leading to permanent discontinuation summarized by system organ class and preferred term

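### Protocol 12.2 keeps AEs on randomized drug after progression out of the AE summary tables, other passages include them, and the SAP neither settles nor declares the difference

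*Protocol*

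**What the plan says.** Patients in either arm may continue randomized drug after RECIST progression if the investigator sees benefit (Protocol 6.1, 7.10 and 9.1.2.1; SAP 1.2.2.2.1). Their AEs are collected until 28 days after they stop (Protocol 9.1.3.3; SAP 1.2.2.3.3).

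For these patients Protocol 12.2 ends by saying that "the AEs occurred in these subjects will be tabulated separately and will not be included in the summary tables of AEs". The same section opens with "All data from the start of treatment until 28 days after the last treatment will be summarized in the safety assessment". Protocol 12.3.3.1 agrees with that opening: "AEs occurring from treatment initiation until 28 days after the last dose will be summarized in the safety evaluation". SAP 5.1 has the same window: "AEs that occur from the start of treatment to within 28 days after the last treatment will be summarized in the safety evaluation".

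The third general principle in SAP 5.1 adds: "Only adverse events during the randomized, double-blind treatment stage and not during the cross-treatment stage are included". On blinding, Protocol 6.2 sets the period as "from the start of randomization until disease progression as assessed by the investigator per RECIST 1.1", and SAP 1.2.6 says that "until the investigator evaluates disease progression based on the RECIST 1.1 criteria, the true status of treatment will be kept blinded". SAP 1.2.2.3.3 gives dosing after progression its own label: "Progression follow-up of subjects who continue to receive the investigational treatment (compassionate treatment) after disease progression".

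SAP section 6 declares one departure from the protocol, the start date for OS. In SAP section 7 the AE tables are not split by progression, and the AE listings are split only by dosing dates.

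**The concern.** One passage excludes a class of on-drug AEs that three others include, and the SAP does not say which applies. Two programmers could produce different AE tables from the same data, each able to cite the documents.

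If the 12.2 sentence is applied, AEs that arise on randomized drug after progression do not reach the main tables. The patients stay in the safety-set denominator (SAP 2.3.3). Their dosing after progression also counts as exposure, because SAP 3.8 runs total exposure from first to last dose. The separate tabulation that 12.2 promises has no counterpart among the SAP outputs. Comparing safety between arms is a stated secondary objective (Protocol 5.1.2, SAP 1.1.2).

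**Working it through.** **1. The passages side by side.** The question is whether an AE that starts on randomized drug after progression enters the summary tables.

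| Place | Answer |
|---|---|
| Protocol 12.2, opening | Yes, by time window |
| Protocol 12.2, last sentence | No |
| Protocol 12.3.3.1 | Yes, by time window |
| SAP 5.1, time window | Yes |
| SAP 5.1, third principle | Unclear: no if the double-blind stage ends at progression, yes if only crossover is meant |
| SAP section 6 | Silent |
| SAP section 7 | No separate table or listing |

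**2. What would be lost.** Protocol 12.3.3.1 counts patients with at least one AE of each kind. A patient with a given AE before progression still counts in that row. What drops out is an AE that first occurs after progression, or one that first reaches its worst grade then.

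**3. How many patients could be concerned.** The documents give no number or share of patients treated after progression, so only a bounded illustration is possible.

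Inputs (Protocol 5.3, SAP 1.2.3): HR 0.67, median PFS 10 and 15 months, 1:1 allocation, 410 patients (205 per arm), accrual A = 8 months, maximum observation T = 23 months, two-sided alpha 0.05, power 90%, 262 events. Uniform accrual and no dropout are my assumptions.

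The plan's own figure reproduces by Schoenfeld's formula: 4(1.960 + 1.282)² / (ln 0.67)² = 262.06, and 262 events give 89.99% power.

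Expected share of an arm with a PFS event at month 23, with λ = ln 2 / median:

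P = 1 − [exp(−λ(T − A)) − exp(−λT)] / (λA)

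- Gefitinib: 1 − (0.3536 − 0.2031)/0.5545 = 0.729, so 205 × 0.7286 = 149 patients.
- HS-10296: 1 − (0.5000 − 0.3455)/0.3697 = 0.582, so 205 × 0.5820 = 119 patients.

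PFS events include deaths, so these counts are upper bounds for patients who could continue after progression. Multiplying P by an assumed share s who continue drug gives the share of each arm with dosing after progression:

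| s gefitinib / HS-10296 (assumed) | Gefitinib arm | HS-10296 arm |
|---|---|---|
| 10% / 10% | 7.3% | 5.8% |
| 30% / 30% | 21.9% | 17.5% |
| 50% / 50% | 36.4% | 29.1% |
| 40% / 10% | 29.1% | 5.8% |
| 10% / 40% | 7.3% | 23.3% |

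The two arms are equal when the HS-10296 share is 0.7286/0.5820 = 1.25 times the gefitinib share. Above that ratio the imbalance reverses. These are shares of patients with some dosing after progression, not shares of AEs lost; the loss on the natural reading is smaller.

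**The case against.** The strongest reply is that the SAP already includes these AEs. Its window has no progression cut-off, and its third principle names only crossover as the excluded stage. Progression does not unblind a patient automatically: Protocol 6.1 and 7.6.1 allow unblinding where later treatment needs it, and 6.1 recommends that the decision to continue be made blinded. This is a fair reading and perhaps the intended one. It does not close the point. Both documents define the blind as lasting until progression, the SAP labels later dosing separately, and section 6 declares no departure from 12.2.

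A second reply is that nothing disappears. Protocol 12.2 promises separate tabulation, collection continues, and List 16.2.7.1 covers all AEs on treatment and for 28 days after. That stands for the listings. It does not put the AEs into any table by arm.

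A third is that separating AEs after progression is defensible, since some patients will by then be unblinded. That also stands, provided that a start date and a parallel table by arm are given. The plan has neither.

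Two stronger readings are tempting. A reader might infer that 12.2 deletes the whole AE history of these patients, including AEs before progression. The wording permits it, but the paragraph goes period by period and the section opens by including all data from the start of treatment, so AEs after progression are the natural meaning. A reader might also infer that the safety comparison is biased in a known direction. Progression is assumed to be more frequent on gefitinib by the cut-off, but only gefitinib patients may cross over (Protocol 9.2), which requires stopping gefitinib. No continuation share is given for either arm.

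**Conclusion.** The contradiction is real and should be resolved. Protocol 12.2 excludes AEs on randomized drug after progression, most naturally from progression onward. Its own opening, Protocol 12.3.3.1 and the SAP 5.1 window include them. The SAP's stage restriction is ambiguous, and no departure is declared.

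If 12.2 is followed, first-occurring or worse-grade AEs after progression leave the main tables while the patients remain in the denominator and in the exposure total. The number concerned is bounded above by about 149 gefitinib and 119 HS-10296 patients at month 23, times an unknown continuation share. This rests on the design's exponential medians, uniform accrual and no dropout. The loss may differ by arm, but the documents determine neither its size nor its direction.

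**What to change.** - In SAP 5.1, state that the AE tables include AEs on randomized drug from first dose through the end of randomized treatment, including treatment after progression, and exclude only the open-label crossover period. In the third principle, refer to randomized treatment rather than to the double-blind stage.
- Delete the last sentence of Protocol 12.2, or declare the departure from it in SAP section 6.
- Flag AEs after progression in the AE listing.
- In the same edit, resolve a separate contradiction. Protocol 12.2 and SAP 5.1 each say both that AEs in the 28 days after the last dose are summarized and that they are kept out of the summary tables. Protocol 12.3.3.1 and the inclusion windows quoted above from those two sections support including them.

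The cost is SAP wording, one entry in section 6 and a flag derived from dates already collected. The small downside is that AEs which may arise after unblinding enter the main tables; the flag lets a reader see them apart.
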